2.2.2 Regulatory Status

Recombinant tissue plasminogen activator is authorized for use by country-specific regulatory agencies in all participating geographies for fibrinolysis of pulmonary embolism.

2.2.3 Drug Preparation and Accountability

The r-tPA used in the study will be procured from standard pharmacy supplies and prepared following pharmacy procedures and the manufacturer's instructions. Pharmacies are experienced in reconstituting and diluting r-tPA for infusion procedures. No special labeling or tracking is required for r-tPA used in this study at US sites but may be required by local agencies for sites outside the US.

3 STUDY OBJECTIVES AND ENDPOINTS

3.1 Objective

The objective is to determine the optimum dose of thrombolytic and duration of the ultrasound procedure (together defined as the APT Procedure) as a treatment for acute submassive PE. Symptomatic submassive PE are patients with acute (≤ 14 days) PE with normal systemic arterial blood pressure (>90 mmHg) and evidence of RV dysfunction (Right Ventricular to Left Ventricular diameter ratio, i.e., RV/LV ratio ≥ 0.9)²⁶.

3.2 Primary Efficacy Endpoint

The primary efficacy endpoint is the change in the ratio of the measurement of the RV/LV as measured by computed tomographic angiography (CTA) from Screening/Baseline to 48 ± 6 hours after the start of the APT Procedure.

3.3 Secondary Efficacy Endpoints

1. Change from Screening/Baseline in echocardiographic parameters including RV/LV ratio, Tricuspid Annular Plane Systolic Excursion (TAPSE), estimated Right Ventricular Systolic Pressure (RVSP), and collapse of the inferior vena cava (IVC) with respiration within 4 hours after the end of the APT Procedure, 24 and 48 hours after the start of the APT Procedure and at 30 days, 90 days and 365 days after the end of the APT Procedure.
2. Change from Screening/Baseline in thrombus burden by modified Miller score as assessed by CTA at 48 hrs. after the start of the APT Procedure.
3. Freedom from major harm occurring between enrolment and 30 days and assessed by the Safety Monitor using the following criteria:
 - a. Mortality – all cause and PE related
 - b. CV collapse: Defined as one or more of the following:
 - i. >40 mmHg drop in SBP (for >15 minutes from documented blood pressure as an in-patient) despite IV fluid challenge and absence of new atrial arrhythmia.

- ii. Requirement for emergency systemic thrombolysis
- iii. Requirement for emergency surgical embolectomy
- iv. Requirement for vasopressors
- v. Intubation/Ventilation

- c. Major bleeding per ISTH
- d. Recurrent PE (confirmed by imaging)
- e. Surgical correction of device related complication

- 4. 6 minute walk test (6MW) distance with BORG score and requirement for oxygen therapy
- 5. Quality of life (QOL) as measured by the Pulmonary Embolism Quality of Life (PEmb-QOL) and EQ-5D-5L at all post-hospitalization subject visits.
- 6. Healthcare resource utilisation during hospitalisation:
 - a. Time from hospital admission to diagnosis of PE
 - b. Time from diagnostic CT scan to initiation of treatment for PE
 - c. Time in each Level of Care (Level 0 and 1; Level 2; and/or Level 3) through discharge. Levels are defined according to National Framework Document.
 - d. Team managing the pt – specialties involved
- 7. Healthcare resource utilisation after hospitalisation and during first 12 months:
 - a. Team managing the pt - specialties
 - b. HCP visits for VTE
 - c. Hospital re-admission frequency and duration

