6.5 Rescue Treatment in Case of Hemodynamic or Ventilatory Collapse

Rescue medications and additional treatment in case of hemodynamic or ventilatory collapse

In the event of hemodynamic or ventilatory collapse, the following emergency supportive and therapeutic measures can be provided at the discretion of the investigator and responsible clinical team:

- Inotropic or vasopressor agents at any dosage regarded necessary
- Rescue peripherally-administered systemic fibrinolytic therapy
- Surgical pulmonary embolectomy
- Catheter-assisted embolectomy including thrombus fragmentation or aspiration
- IVC filters

Of note, reperfusion techniques including rescue fibrinolytic therapy, emergency surgical pulmonary embolectomy, or emergency catheter-assisted embolectomy should not be performed unless the subject suffers hemodynamic collapse. The recommendation is consistent with current treatment guidelines which discourage the use of these advanced therapies for hemodynamically stable subjects with acute PE²⁷. Rescue fibrinolysis, surgical pulmonary embolectomy, and catheter-assisted embolectomy should be recorded in the eCRF.

Inferior vena cava filter insertion

The insertion of IVC filters is discouraged unless the subject develops a contraindication to therapeutic-dose systemic anticoagulation or if the subject suffers recurrent PE despite therapeutic levels of anticoagulation. If an IVC filter is placed, the procedure should be noted in the appropriate section of the eCRF.

6.6 24, 48 And 72 Hours After the Start of the APT Procedure

At 24 hours (± 6 hours) after the start of the APT procedure, the following assessments will be performed.

1. Vital signs (systolic/diastolic blood pressure, heart rate, respiratory rate, and SpO₂)
2. PESI score (sPESI will be calculated from PESI)
3. Adverse/VTE/Bleeding Events

At 48 hours (± 6 hours) after the start of the APT procedure, the following assessments will be performed.

1. Vital signs
2. PESI score (sPESI will be calculated from PESI)
3. Prior to CTA: Laboratory Tests and biomarkers
 - a. Hgb, Hct, BUN, creatinine and bleeding tests per Standard of Care based on anticoagulant therapy
 - b. D-dimer, BNP/NT-proBNP, lactate/lactic acid and troponin
4. CTA to obtain RV/LV ratio and Modified Miller Score
5. Echocardiogram to measure: RV/LV ratio, TAPSE, estimated RVSP, and collapse of the IVC with respiration
6. Adverse/VTE/Bleeding events

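### The 30-day freedom-from-major-harm composite counts emergency systemic thrombolysis and surgical embolectomy but not emergency catheter-assisted embolectomy, which Protocol 6.5 lists as rescue on the same terms

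*Protocol*

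**What the plan says.** Protocol 3.3, item 3, defines the endpoint as "Freedom from major harm occurring between enrolment and 30 days and assessed by the Safety Monitor using the following criteria". The criteria are death, CV collapse, ISTH major bleeding, recurrent PE confirmed by imaging, and surgical correction of a device complication.

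Criterion 3b reads "CV collapse: Defined as one or more of the following", and gives five items:

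- Item i is a fall of more than 40 mmHg, worded as "drop in SBP (for >15 minutes from documented blood pressure as an in-patient) despite IV fluid challenge and absence of new atrial arrhythmia".
- Item ii is systemic thrombolysis needed as an emergency.
- Item iii is "Requirement for emergency surgical embolectomy".
- Item iv is a need for vasopressor support.
- Item v is intubation or ventilation.

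The same list appears in the Protocol synopsis and 10.3.2, and in the SAP synopsis, 1.3, 2.3.2 and Appendix 1 item 26. Catheter-assisted embolectomy is in none of them.

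Protocol 6.5 sets out the measures available for hemodynamic or ventilatory collapse. Beside systemic fibrinolysis and surgical embolectomy it lists "Catheter-assisted embolectomy including thrombus fragmentation or aspiration". It restricts all three reperfusion techniques to hemodynamic collapse and adds: "Rescue fibrinolysis, surgical pulmonary embolectomy, and catheter-assisted embolectomy should be recorded in the eCRF". SAP Appendix 1 item 20 reports the Rescue Therapy CRF as a by-patient listing sorted by arm. Nothing links that listing to item 26.

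**The concern.** The composite counts two of the three rescue reperfusion techniques that the protocol groups together, and neither document says why the third is left out. The Safety Monitor works from a closed list, so a patient who needed an emergency catheter embolectomy can be recorded as free of major harm.

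This matters because Protocol 11.2 names ineffective treatment, from limiting the r-tPA dose and infusion time, as a risk of the study. A need for further reperfusion is a direct sign of that. An endpoint meant to summarise major harm should not miss one form of it through wording. As written, the omission can only raise the reported freedom rate; it cannot lower it.

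**Working it through.** The plan gives no figure for this endpoint, so there is none to reproduce. The check compares the two lists and then works out a scale.

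**Step 1. Rescue measures in Protocol 6.5 against the composite**

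| Reperfusion rescue in 6.5 | Restricted to hemodynamic collapse | Recorded in eCRF | Counted in 3b |
|---|---|---|---|
| Systemic fibrinolysis | yes | yes | yes (ii) |
| Surgical embolectomy | yes | yes | yes (iii) |
| Catheter-assisted embolectomy | yes | yes | no |

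**Step 2. Could another criterion always catch a catheter-rescued patient?**

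- Item i needs a fall of more than 40 mmHg for more than 15 minutes, despite fluids and without new atrial arrhythmia. A fall from 125 to 88 mmHg is 125 − 88 = 37 mmHg and does not qualify, although 88 is below the 90 mmHg limit in the exclusion criteria (Protocol 5.2). In general, any starting pressure of 129 mmHg or less can reach 89 with a fall of at most 129 − 89 = 40 mmHg. A shorter fall, or one with new atrial arrhythmia, also fails item i.
- Items iv and v do not apply if the catheter rescue comes before, or without, vasopressors and intubation.
- Recurrent PE: Protocol 3.4.2.2 looks for a new filling defect against the baseline CTA. Catheter rescue for persisting original clot would not meet that.
- Criterion e covers only surgical correction of a device complication.

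So a route through the list with no event exists. It needs a patient judged to be in collapse who meets none of these criteria, and who has no death, major bleed, systemic thrombolysis or surgical embolectomy.

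**Step 3. Scale**

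Inputs: 29 subjects enrolled in the UK extension (SAP synopsis) and three arms. 29/3 = 9.7, so about 10 per arm if balanced; the arm sizes are not given. Item 26 has no asterisk, so it is not among the analyses marked for pooling with the earlier 100 treated subjects.

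One reclassified patient moves a rate by 1/n. The table supposes that nobody else has an event. Intervals are 95% Wilson, the method the SAP names for its safety proportions; it names none for this composite. With p = x/n and z = 1.96, the limits are [p + z²/2n ± z√(p(1 − p)/n + z²/4n²)] / (1 + z²/n).

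| n | Patient scored free | Patient counted | Shift (points) |
|---|---|---|---|
| 10 (one arm, assumed) | 10/10 = 100% (72.2 to 100) | 9/10 = 90% (59.6 to 98.2) | 10.0 |
| 25 (planned evaluable per arm) | 25/25 = 100% (86.7 to 100) | 24/25 = 96.0% (80.5 to 99.3) | 4.0 |
| 29 (all UK subjects) | 29/29 = 100% (88.3 to 100) | 28/29 = 96.6% (82.8 to 99.4) | 3.4 |

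With 0, 1 or 2 such patients in an arm of 10, the shift is 0, 10 or 20 points. The documents do not say which applies.

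**Step 4. Timing**

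The SAP gives enrolment as ending in March 2019 and is itself dated 08 November 2019. Every subject's 30-day window had closed by then.

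**The case against.** The strongest reply is that section 6.5 allows catheter rescue only in hemodynamic collapse. A patient treated within the protocol is therefore already very ill, and three of the five collapse items (blood pressure, vasopressors, intubation or ventilation) do not depend on which reperfusion technique is chosen. Most such patients would count anyway. This stands as a limit on how often the gap can matter. It does not close the gap, because section 6.5 gives no definition of hemodynamic collapse and no link to criterion 3b. Systemic thrombolysis and surgical embolectomy carry the same restriction and are still counted as items of their own.

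The second reply is that the event stays visible. Item 20 lists rescue therapies by patient and arm, and a collapse needing rescue would ordinarily be an SAE, tabulated through Day 30 and Day 365. With 29 subjects a reader could find it. This also stands: the event is missing from one composite, not from the report.

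A reader might infer that the omission favours the shorter regimens, because staff who know the arm would choose the uncounted rescue. The documents do not support that. They give no rescue rates by arm. Protocol 6.3.4 allows surgeons as well as cardiologists and radiologists to perform the procedure, and section 6.5 leaves rescue to the investigator and the responsible clinical team. A reader might also infer that inotropes, which section 6.5 names together with vasopressors, must be counted too. Sharing a line in a treatment list does not oblige an endpoint to count both.

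**Conclusion.** The omission is real and consistent across both documents. As written, the rule can score a catheter-rescued patient as free of major harm. The gap is probably narrow and its frequency is unknown; it may be zero. If it occurs, each patient moves an arm's rate by about 10 percentage points, on the assumption that the 29 UK subjects split evenly over three arms.

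It would go too far to say that the score depends only on which rescue the team picks, or that the comparison between arms is biased. The first ignores the items that do not depend on the technique, and the second has no figure behind it. The endpoint is secondary, so the primary efficacy analysis, the primary safety outcome and the sample size are unaffected. The point concerns how an outcome is classified, not how any patient should be treated.

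**What to change.** Keep the prespecified composite as defined, as the main result for this endpoint. In SAP 2.3.2 and Appendix 1 item 26, add a second row in the same subject set: the prespecified criteria, or emergency catheter-assisted embolectomy between enrolment and 30 days. Derive it from the rescue data that Protocol 6.5 already requires in the eCRF (Rescue Therapy CRF, item 20). First confirm that the form identifies the procedure and lets it be placed in the 30-day window, since its questions are not reproduced in the documents. Label the row as added after enrolment closed, so that nobody takes it for the prespecified endpoint.

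Also reconcile criterion 3b with section 6.5: either note that the supplementary row covers the third rescue technique, or state why it is left out of the composite.

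The cost is one extra derivation and one table row, with no new data collection. The expanded rate may look slightly less favourable than the prespecified one.

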3.4 Safety Endpoints

3.4.1 Primary Safety Outcome

The primary safety outcome is frequency of major bleeding within 72 hours after initiating the APT Procedure. Evaluation of clinically overt bleeding will depend upon the suspected bleeding site and clinician's judgment. Major bleeding events will be defined according to the International Society on Thrombosis and Haemostasis (ISTH) criteria for major bleeding

- 1. Fatal bleeding and/or
- 2. Symptomatic bleeding in a critical area or organ (intracranial, intraspinal, intraocular, retroperitoneal, intra-articular or pericardial, or intramuscular with compartment syndrome) and/or

3. Bleeding causing a fall in hemoglobin level of 20 g/L or more, or leading to transfusion of two or more units of whole blood or red blood cells

Major bleeding events will be categorized as in-hospital and/or taking place within 72 hours from the start of the APT Procedure or at time of hospital discharge (whichever is earlier).

3.4.2 Secondary Safety Outcomes

3.4.2.1 Technical procedural complications

Technical complications associated with the use of the EkoSonic® device will be recorded during catheter placement in the pulmonary artery and during the infusion procedure. Any significant dissection or perforation of the pulmonary arteries will be visible on the follow-up CTA.

3.4.2.2 Symptomatic recurrent PE

For the diagnosis of symptomatic recurrent PE throughout the study, documentation of clinical symptoms and/or signs suggesting recurrent PE is required in combination with objective confirmation with CTA, ventilation-perfusion lung scanning, or invasive contrast PAgm. Specifically, symptomatic recurrent PE will be diagnosed if a new filling defect (compared with the Screening/Baseline CTA) is demonstrated on CTA or invasive contrast PAgm.

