The OPTALYSE PE study is designed to investigate the lowest r-tPA dose-ultrasound treatment time required to achieve the same reductions in thrombus burden and associated improvement in physiologic parameters demonstrated in ULTIMA and SEATTLE II. Results of this study are intended to inform the study design for further studies of the APT Procedure. Analysis of the first 100 evaluable subjects in the U.S. study suggested equipoise between Arms 1, 2 and 3 of the protocol and therefore the sample size has been extended and additional sites in the UK National Health Service included, with a view to adding to the findings of the OPTALYSE study from sites in the UK and increasing the number of patients treated by treatment protocol.

Following the initial hospitalization, subjects will be followed for 12 months. The purpose of this follow-up is to obtain information on recurrence of venous thromboembolic events (VTE) and chronic thromboembolic pulmonary hypertension (CTEPH).

2 EKOSonic® ENDOVASCULAR DEVICE and r-tPA

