Placement of the EKOS catheter will be guided by focused PAgm and/or CTA scan. Following successful placement of the EKOS catheter, the APT Procedure will be initiated with r-tPA and the ultrasound started simultaneously. Within four hours after the end of the APT Procedure, subjects will have an echocardiogram obtained. A repeat CTA will be obtained at 48 hours (± 6 hours) after the start of the APT Procedure. Echocardiograms will be obtained at 24 hours (± 6 hours) and at 48 hours (± 6 hours) after the start of the APT Procedure. Vital signs and hemodynamic measurements will be recorded as specified in Sections 7.4 and 7.5.

Integrated bedside assessments will only be obtained at select participating institutions by collecting vital signs and limited echocardiograms (RV/LV ratio only) at frequent intervals from the start of the APT Procedure through 4 hours after its completion to evaluate the possibility of developing a non-invasive PE response evaluation tool for use at the bedside (see Section 7.8). This collection of vital signs and echocardiograms will be reviewed to determine if there is a correlation with the change in clinical parameters and the change in markers of RV strain. The collection of routine bedside vital signs and limited echocardiograms (RV/LV ratio only) do not increase the potential risk to the patients participating in the study. They are non-invasive measurements that will be collected at a higher frequency than normal.

Bleeding, recurrent PE and serious adverse events will be collected and reported throughout the study. Specific reporting for bleeding events will occur during the first 72 hours from the start of treatment or at the time of discharge from the hospital, whichever is earlier.

All imaging studies will be provided to the Core Imaging Laboratory. Procedures for transfer of images from study sites to the Laboratory will be provided in the Syntactx Manual of Operations. Results of the assessments will be entered into the clinical database by the Core Imaging Laboratory.

Subjects will return for follow-up clinic evaluations at 30 (± 5 days), 90 (± 10 days), and 365 (± 14 days) days. It is imperative that contact with subjects be made at the designated times during the study and the status of all subjects is known at 365 days after the Procedure. Subjects will be asked to provide three different means of contact in order to insure an ability to learn the subject's status.

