5 STUDY POPULATION

5.1 Inclusion Criteria

Subjects must meet the following criteria to be eligible for participation in this clinical trial:

1. Male or female ≥ 18 years of age and ≤ 75 years of age
2. CTA evidence of proximal PE (filling defect in at least one main or lobar pulmonary artery)
3. PE symptom duration ≤ 14 days
4. Submassive PE: RV/LV diameter ≥ 0.9 from CTA, hemodynamically stable and an elevated biomarker.
5. Treatment must be started within 48 hours of diagnosis of PE by CTA.
6. Signed Informed consent obtained from subject or Legally Authorized Representative.

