7.2 Physical Exam and Patient Information

Data from routine physical examination of the patient will be documented at Screening/Baseline prior to study enrollment. The physical exam will include an assessment of all major body systems. Significant findings will be recorded in the subject's Medical History according to the Investigator's clinical judgment.

Patient demographics, medical history and VTE risk factors will be obtained and documented on the eCRF. If physical examination findings and/or patient information are available from initial admission notes, a repeat of these assessments is not required.

7.3 *Electrocardiogram*

A 12-lead ECG will be performed at Screening/Baseline. If an ECG has already been performed for this PE event, a repeat ECG is not required.

7.4 *Vital Signs*

Vital signs including, systolic/diastolic blood pressure, heart rate, respiratory rate, and SpO2 will be recorded at Screening/Baseline, at the start and at the conclusion of the APT procedure, within 4 hours Post-APT Procedure, at 24 (\pm 3) hours and 48 (\pm 6) hours after the start of the APT Procedure, and at all clinic visits. Temperature will be recorded for the purpose of completing the PESI/sPESI score at Screening/Baseline, within 4 hours, and at the 24 and 48 hour time points when the echocardiograms are performed

7.5 *Right Heart Hemodynamic and SvO2 Measurements (Optional)*

It is recommended that baseline right-heart pressures including mean right atrial, right ventricular systolic and diastolic, and main pulmonary artery systolic, diastolic and mean pressures, as well as mixed venous O2 saturation (SvO2) are obtained immediately prior to APT treatment.

7.6 *Computed Tomography Pulmonary Angiography (CTA)*

CTA will be performed at Baseline/Screening and at 48 (\pm 6) hours after the start of the APT Procedure to evaluate change in the RV/LV diameter ratio and thrombus burden (modified Miller Score).

7.7 *Echocardiogram*

An echocardiogram will be obtained at Screening/Baseline, within 4 hours Post-APT treatment, 24 (\pm 6) hours and 48 (\pm 6) hours after the start of the APT Procedure, and at 30 (\pm 5 d), 90 (\pm 10 d) and 365 (\pm 14 d) day clinic visits to evaluate RV/LV ratio, TAPSE, estimated RVSP, and collapse of the IVC with respiration.

7.8 *Integrated Bedside Assessment (Select Participating Sites Only)*

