1.4.2.2 Symptomatic recurrent PE

For the diagnosis of symptomatic recurrent PE throughout the study, documentation of clinical symptoms and/or signs suggesting recurrent PE is required in combination with objective confirmation with CTA, ventilation-perfusion lung scanning, or invasive contrast PAgram. Specifically, symptomatic recurrent PE will be diagnosed if a new filling defect (compared with the baseline CTA) is demonstrated on CTA or invasive contrast PAgram.

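### The pre-treatment CTA is the stated reference for a new filling defect throughout follow-up, so recurrent PE after the 48-hour CTA can be misclassified in either direction

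*Protocol*

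**What the plan says.** Protocol 3.4.2.2 requires symptoms or signs together with objective confirmation by CTA, ventilation-perfusion scanning or invasive angiography. It then gives the imaging criterion: "symptomatic recurrent PE will be diagnosed if a new filling defect (compared with the Screening/Baseline CTA) is demonstrated on CTA"; invasive angiography is judged the same way. SAP 1.4.2.2 has the same rule: "symptomatic recurrent PE will be diagnosed if a new filling defect (compared with the baseline CTA) is demonstrated on CTA". Both sections apply it for the whole study and neither introduces a later reference scan.

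The baseline scan shows proximal clot in every eligible patient. Protocol 5.1 requires "CTA evidence of proximal PE (filling defect in at least one main or lobar pulmonary artery", and Protocol 6.3.2 starts treatment within 48 hours of that scan. A post-treatment scan is also planned. Protocol section 4 says "A repeat CTA will be obtained at 48 hours", and Protocol 7.6 gives its purpose as "to evaluate change in the RV/LV diameter ratio and thrombus burden (modified Miller Score". Protocol 3.3, item 2, uses it for an endpoint: "Change from Screening/Baseline in thrombus burden by modified Miller score as assessed by CTA at 48 hrs".

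Recurrent PE is reported as a proportion with a 95% interval to day 365 (Protocol 10.4; SAP 2.4, which specifies Wilson). Item 23 of the safety tables in SAP Appendix 1 asks for imaging confirmation and names no comparator. The recurrent-PE component of 30-day freedom from major harm is worded the same way (Protocol 3.3, item 3d).

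**The concern.** A pre-treatment scan is a natural reference for the first hours. It is a weak one for the following year, because treatment is meant to clear the very defects that the scan shows. After the 48-hour CTA, the question is whether clot has appeared since the patient was last imaged. A comparison with baseline answers a different question.

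The outcome matters within this plan. On the 12-month follow-up, Protocol 1.2 says: "The purpose of this follow-up is to obtain information on recurrence of venous thromboembolic events (VTE". At stake is the classification of a handful of events in a small cohort, reported by arm. No hypothesis test depends on it.

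A better reference already exists. The adjacent outcome, technical complications, already looks to the post-treatment scan: "Any significant dissection or perforation of the pulmonary arteries will be visible on the follow-up CTA". That sentence concerns vessel injury, so it shows only that the scan is available for safety reading, not that it was meant as the reference for recurrence.

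**Working it through.** The plan states no figure to reproduce: no recurrence rate, no share of recurrences at cleared sites, and no size for the safety set by arm. The check is therefore mainly of the text, followed by an illustration of scale.

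**Step 1: apply the two rules to one arterial site.** In each row the event scan is done for symptoms and shows a filling defect. The alternative rule calls a defect new if the site was clear on the most recent available CTA before the event.

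| Baseline CTA | 48-hour CTA | Baseline rule | Latest-scan rule |
|---|---|---|---|
| clear | clear | new | new |
| filled | filled | not new | not new |
| filled | clear | not new | new |
| clear | filled, no symptoms | new | not new |
| filled | filled, then clears without a scan | not new | not new |
| filled | event precedes this scan | not new | not new |

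The rules differ in rows 3 and 4, and in opposite directions. Row 3 is a possible under-count and row 4 a possible over-count. Nothing in the documents says which is more frequent, so the net sign is unknown. Rows 5 and 6 show what a change of reference cannot repair.

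**Step 2: scale of one reclassified event.** Inputs: 29 enrolled in the UK extension (SAP synopsis, Enrollment); three arms; tabulation by arm for the UK extension unless otherwise specified (SAP 2.2 and Appendix 1). Item 23 has no asterisk, so it is not marked for pooling with the earlier cohort. Assumption: a near-equal split, 29/3 = 9.7, so about 10 per arm, with 8 to 12 as a range. Event counts of 0 and 1 are also assumed.

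Wilson 95% interval, with p = x/n and z = 1.96 (z² = 3.84):

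- centre = (p + z²/2n) / (1 + z²/n)
- half-width = z √[p(1 − p)/n + z²/4n²] / (1 + z²/n)

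For 1/10, the centre is (0.100 + 0.192)/1.384 = 0.211 and the half-width is 1.96 × √(0.0090 + 0.0096)/1.384 = 0.193, giving 1.8 to 40.4%. For 0/10, the upper limit is 3.84/13.84 = 27.8%.

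| Assumed n per arm | 1 event | 0 events | Difference in upper limit |
|---|---|---|---|
| 8 | 2.2 to 47.1% | 0 to 32.4% | 14.7 points |
| 9 | 2.0 to 43.5% | 0 to 29.9% | 13.6 points |
| 10 | 1.8 to 40.4% | 0 to 27.8% | 12.7 points |
| 11 | 1.6 to 37.7% | 0 to 25.9% | 11.9 points |
| 12 | 1.5 to 35.4% | 0 to 24.3% | 11.1 points |

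Over all 29 patients, 1 event gives 3.4% (0.6 to 17.2%) and 0 events give 0% (0 to 11.7%). The shift runs downwards for a row 3 event and upwards for a row 4 event. Any binary outcome would move by this amount in arms of this size, so the table shows sensitivity to one event and says nothing about how often the rule misclassifies.

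**The case against.** The strongest reply is that the text does not exclude anything. The criterion says when recurrence will be diagnosed; it does not say only then. Ventilation-perfusion confirmation is allowed with no comparator. The reporting table and the major-harm component ask only for imaging confirmation, which clot returning at a cleared site would satisfy. All of this stands, and it makes the problem one of literal reading rather than certain omission. It does not remove the problem: the only stated imaging criterion for a new defect is the baseline one, it appears in both documents, and the person classifying the event is given no other.

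A reader might infer that recurrent PE is bound to be understated. The documents do not support that, because the same rule can also count a defect that was already there without symptoms at 48 hours. A reader might also infer that safety information is lost. It is not: recurrent VTE is collected among serious adverse events to day 365 (Protocol 6.7), and the safety monitor adjudicates all serious adverse events (Protocol 8.13). Finally, one might infer a bias between arms, on the ground that clearance could differ by regimen. The documents give no data on this, so it remains conjecture.

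**Conclusion.** The concern holds as a possible misclassification, in both directions, of recurrent PE after the 48-hour CTA. It directly affects one descriptive secondary safety outcome, and possibly the recurrent-PE component of 30-day major harm, where no comparator is stated. Primary efficacy, primary safety, power and alpha do not depend on it.

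Neither the size nor the sign of the net effect can be derived from the documents. The interval shifts of about 11 to 15 points in the upper limit rest on assumed arm sizes of 8 to 12 and exactly one reclassified event; they are not an estimate of the effect. Priority lies between an optional clarification and a recommended change. The low cost argues for making it.

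**What to change.** In Protocol 3.4.2.2 and SAP 1.4.2.2, define a new filling defect on CTA or angiography as one at a site that was clear on the most recent available CTA before the event. That is a later unscheduled CTA if one was done, otherwise the 48-hour CTA, otherwise the Screening/Baseline CTA. Keep the requirement for symptoms or signs. Apply the same definition to item 23 of the safety tables in SAP Appendix 1 and to the recurrent-PE component of major harm. Because enrolment has ended, also report the count under the existing baseline rule, so that any effect of the change is visible.

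The cost is a short text change in each place and a site-level look at existing scans for the few suspected recurrences; no new procedure is needed. That look may be extra work: SAP Appendix 1 plans clot locations only for the baseline scan, and a modified Miller score at 48 hours does not by itself show that a per-site reading exists. The reference scan will also differ between patients.

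Two gaps remain. Events before the 48-hour CTA normally keep the baseline reference, and clot that clears after the last available scan and then returns is still not identified.
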